8.0 Expected Duration of Study

Surveillance period: May 2013 to September 30, 2016

Patient enrollment period: May 2013 to May 31, 2015*

*Enrollment may be closed before the end of the enrollment period if the total number of patients enrolled in the Study reaches the target sample size.

9.0 Survey Items

The investigator will enter the information of the following items into **CCI** [REDACTED]. The schedule for the Study is provided in the Appendix.

9.1 Patient Enrollment

1) Survey items

Prescription date of the Date, patient ID number, patient initials, sex, birth date, determination with inclusion criteria, and determination with exclusion criteria

2) Survey timing

The time of patient enrollment

9.2 Patient Demographics

1) Survey items

Height, weight, time of hyperlipidemia diagnosis, treatment category, menopausal status (only for female), complications (presence or absence and details), medical history (presence or absence and details), hypersensitivity disposition (presence or absence and details), drinking history, smoking history, presence or absence of surgery within one month before baseline, and presence or absence of healthier lifestyle education (diet and exercise therapies)

2) Survey time

Baseline

9.3 Treatment Information

1) Survey items

Administration of the Drug (daily dose, treatment duration, and status of completion of treatment with the Drug), administration of antihyperlipidemic drugs other than the Drug* (presence or absence, drug name, daily dose, and treatment duration), and administration of concomitant medications (other than antihyperlipidemic drugs) (presence or absence, drug name, and purpose of administration)

*: Including antihyperlipidemic drugs with which treatment is discontinued within two months before baseline.

2) Survey timing

Period from baseline to Month 12 (or discontinuation of treatment)

9.4 Testing/Observation Items

1) Survey items

Triglyceride (TG), total cholesterol (TC), LDL cholesterol* (LDL-C), HDL cholesterol (HDL-C), VLDL cholesterol (VLDL-C), Apo-AI, Apo-B, Apo-CIII, lipoprotein a, remnant lipoprotein cholesterol (RLP-C), fasting blood glucose (FBG), HbA1c *: When tested by direct measurement

2) Survey timing

Baseline, Month 3, Month 6, Month 9, and Month 12 (or discontinuation of treatment) test timepoints

9.5 Other Observation Items

1) Survey items

Pregnancy status

If the patient is found to be pregnant during the observation period, the investigator will report the Takeda MR. The investigator will, upon request from the Takeda MR, use a sheet for pregnant women to provide detailed information (including information available up to childbirth, including premature birth or other pregnancy results, if possible).

2) Survey timing

Period from baseline to Month 12 (or discontinuation of treatment)

9.6 Adverse Events (AEs)

1) Survey items

Presence or absence of AE (see Table 1), AE name, date of onset, seriousness and reason for seriousness (see Table 2), action taken to the Drug, date of determination of outcome, outcome, and causal relationship to the Drug* (see Table 3)

If the outcome is not resolved or unknown and the causal relationship is determined as unevaluable, follow-up survey should be conducted to some extent possible.

*If causal relationship to the Drug is determined as not related, reasons that may constitute the rationale for determination should be collected if it is unevaluable.

2) Survey timing

Period from baseline to Month 12 (or discontinuation of treatment)

3) Priority survey item

Bleeding-related events occurring after baseline are set as a priority survey item. If any bleeding-related event is reported as an AE, laboratory test values related to bleeding should be separately collected.

Table 1 Definition of Adverse Event

An adverse event (AE) is any untoward medical occurrence in a patient administered a medicinal product and which does not necessarily have to have a causal relationship with this treatment.
An AE can therefore be any unfavorable and unintended sign (including an abnormal laboratory finding, for example), symptom, or disease temporally associated with the use of a medicinal product, whether or not considered related to the medicinal product.
The following should be also handled as an AE:

• A symptom or other problem occurring in an infant breastfed from a mother taking the medicinal product• A symptom or other problem occurring in a child administered the medicinal product• A symptom or other problem occurring in a patient administered or taking more than the approved dose of the medicinal product

Table 2 Seriousness Criteria

An event is classified as serious if:
1. resulting in death (death),
2. being life-threatening (at risk of death),
3. requiring inpatient hospitalization or prolongation of existing hospitalization (hospitalization/prolonged hospitalization),
4. resulting in persistent or significant disability/incapacity (disorder),
5. being a congenital anomaly/birth defect (birth defect), or
6. being any other medically serious condition that does not fall under any of 1 to 5 above. Note that all those listed in the Takeda Medically Significant AE List are included in this criterion. (Examples include bronchospasm, which requires short-term intensive care in emergency room settings.)

Takeda Medically Significant AE List

• Acute respiratory failure/acute respiratory distress syndrome (ARDS)	• Anaphylactic shock
• Torsade de pointes/ventricular fibrillation/ventricular tachycardia	• Acute renal failure
• Malignant hypertension	• Pulmonary hypertension
• Convulsive seizure (including spasm and epilepsy)	• Pulmonary fibrosis (including interstitial lung disease)
• Agranulocytosis	• Neuroleptic malignant syndrome/malignant hyperthermia
• Aplastic anaemia	• Spontaneous abortion/stillbirth and foetal death
• Toxic epidermal necrolysis/muco-cutaneo-ocular syndrome (Stevens-Johnson syndrome)	• Confirmed or suspected transmission of infection by a medicinal product
• Hepatic necrosis	• Confirmed or suspected endotoxin shock
• Acute hepatic failure	

Table 3 Criteria for Casual Relationship between Adverse Event and the Drug

Determination	Criteria
Related (if the Drug is suspected to have contributed to the event)	There is temporally evident correlation between the Drug and the event (including results from discontinuation of treatment). Or the event is an AE considered likely to have been caused by the Drug although it is presumed to have been contributed by other factors, such as primary disease, complications, concomitant medications, or combined treatments.
Not related (if the Drug is considered unlikely to have contributed to the event)	There is no temporally evident correlation between the Drug and the event. Or the event is adequately considered to have been contributed by other factors, such as primary disease, complications, concomitant medications, or combined treatments.
Unevaluable	There is lack of information necessary for evaluation of the event, including temporal correlation (including results from discontinuation of treatment), primary disease, complications, concomitant medications, and combined treatments.

10.0 Analysis Items and Method

10.1 Patient Disposition Items

Compile information including the number of enrolled patients, number of patients with eCRFs collected, numbers of safety- and efficacy-evaluable patients, and the number of patients excluded from analysis and reasons for exclusion.

10.2 Patient Demographics

Compile patient demographic information including sex, age, hypersensitivity disposition, and complications.

10.3 Treatment Details

Compile information on administration of the Drug and of concomitant medications.

10.4 Safety Items

Compile the following regarding the safety-evaluable population. AEs, coded using MedDRA, will be summarized by preferred term (PT) and by system organ class (SOC).

10.4.1 Onset Status of Adverse Events

Compile the incidence of AEs occurring during the observation period, in terms of, e.g., causal relationship with the Drug, type, seriousness. Note that bleeding-related events should be separately compiled because such events are set as a priority survey item.

10.4.2 Factors Likely to Affect Safety

Compile the incidence of ADRs occurring during the observation period, by stratification variables: patient baseline characteristics (sex, age, presence or absence of renal

dysfunction, presence or absence of hepatic dysfunction, etc.) and treatment regimen (administration of the Drug, administration of concomitant medications such as anticoagulant drugs, antiplatelet drugs).

10.5 Efficacy Items

Compile the following regarding the efficacy-evaluable population.

10.5.1 Changes in Lipid Parameters: TG, TC, LDL-C, HDL-C, Non-HDL-C, etc.

Tabulate observed values and changes (observed value at each observational timepoint after baseline minus observed value at baseline) at each observational timepoint for TG, TC, LDL-C (by converted value calculated by direct measurement, Friedewald formula*), HDL-C, Non-HDL-C (converted value**), VLDL cholesterol, Apo-AI, Apo-B, Apo-CIII, lipoprotein a, and RLP-C.

*: $LDL-C = TC - HDL-C - TG / 5$

**: $Non-HDL-C = TC - HDL-C$

Note that LDL-C, Non-HDL-C, TC/LDL-C ratio, LDL-C/HDL-C ratio, and LDL-C/Apo-B ratio should be calculated from test results.

10.5.2 Factors Likely to Affect Efficacy

Compile TG values by stratification variables: patient baseline characteristics (sex and age) and treatment regimen (administration of the Drug, administration of concomitant medications, etc.).

13.0 Other Necessary Items

13.1 Protocol Revision

During the surveillance period, keep track of, e.g., the progress of the Study, the onset of unexpected ADRs or serious ADRs based on the precautions, presence or absence of increased incidence of specified ADRs, the appropriateness of survey items. If needed, review and revise this protocol. If partial change approval is obtained for dosage and administration or indications during the surveillance period, examine whether to revise this protocol if necessary and revise it if necessary.

13.2 Action Taken in Case of Problem or Question

If any problem is found in the safety or efficacy of the Drug, carefully review the data and examine what needs to be done.

Appendix Study Schedule

Survey Item		Survey and Data Entry Timing		Observation Period				
		Patient enrollment	Baseline	Month 3	Month 6	Month 9	Month 12	Discontinuation
Patient Enrollment	Prescription date of the Drug	○						
Patient Enrollment	Patient ID number	○						
Patient Enrollment	Patient initials	○						
Patient Enrollment	Sex	○						
Patient Enrollment	Birth date	○						
Patient Enrollment	Inclusion criteria/exclusion criteria	○						
Patient Demographics	Height, Weight		○					
Patient Demographics	Time of hyperlipidemia diagnosis		○					
Patient Demographics	Treatment category		○					
Patient Demographics	Menopausal status (only for female)		○					
Patient Demographics	Complications		○					
Patient Demographics	Medical history		○					
Patient Demographics	Hypersensitivity disposition		○					
Patient Demographics	Drinking history, smoking history		○					
Patient Demographics	Presence or absence of surgery before baseline		○					
Patient Demographics	Presence or absence of healthier lifestyle education (diet and exercise therapies)		○					
Treatment Information	Administration of the Drug			○	→			○
Treatment Information	Administration of other antihyperlipidemic drugs		←	○	→			○
Treatment Information	Administration of concomitant medications (other than antihyperlipidemic drug)		←	○	→			○
Testing /Observation Items	TG		○	○	○	○	○	○
Testing /Observation Items	TC		○	○	○	○	○	○
Testing /Observation Items	LDL-C (direct measurement)		○	○	○	○	○	○
Testing /Observation Items	HDL-C		○	○	○	○	○	○
Testing /Observation Items	VLDL-C		○	○	○	○	○	○
Testing /Observation Items	Apo-AI		○	○	○	○	○	○
Testing /Observation Items	Apo-B		○	○	○	○	○	○
Testing /Observation Items	Apo-CIII		○	○	○	○	○	○
Testing /Observation Items	Lipoprotein a		○	○	○	○	○	○
Testing /Observation Items	RLP-C		○	○	○	○	○	○
Testing /Observation Items	FBG		○	○	○	○	○	○
Testing /Observation Items	HbA1c		○	○	○	○	○	○
Testing /Observation Items	Pregnancy status (only for female)		←	○	→			○
Testing /Observation Items	AE		←	○	→			○

○: Surveyed, tested, or observed ← ○ → Surveyed, tested, or observed throughout the period

1.0 Definitions of Terms

1.1 Definitions

Item	Definition
Survey unit period (periodic safety report)	Periodic Safety Report 1: July 22, 2012 to January 21, 2013 Periodic Safety Report 2: January 22, 2013 to July 21, 2013 Periodic Safety Report 3: July 22, 2013 to January 21, 2014 Periodic Safety Report 4: January 22, 2014 to July 21, 2014 Periodic Safety Report 5: July 22, 2014 to July 21, 2015 Periodic Safety Report 6: July 22, 2015 to July 21, 2016 Periodic Safety Report 7: July 22, 2016 to July 21, 2017 Periodic Safety Report 8: July 22, 2017 to July 21, 2018
Drug	Lotriga Granular Capsules
SOC	System organ class of MedDRA.
HLGT	High level group term of MedDRA.
PT	Preferred term of MedDRA.
LLT	Lowest level term of MedDRA.
Enrolled patient	A patient approved for enrollment in the Study.
Patient with eCRF collected	An enrolled patient whose eCRF was submitted via CCI .
Patient with eCRF uncollected	An enrolled patient other than a patient with eCRF collected.
Locked patient	A patient who has completed the approval process in the PMS system.
Unlocked patient	A patient with eCRF collected other than a locked patient.
Safety-evaluable patient	A locked patient included in safety evaluation.
Safety-unevaluable patient	A locked patient excluded from safety evaluation.
Efficacy-evaluable patient	A safety-evaluable patient included in efficacy evaluation.
Efficacy-unevaluable patient	A safety-evaluable patient excluded from efficacy evaluation.
ADR	An abbreviated form of the term ‘adverse drug reaction or infection.’ Refers to an adverse event other than those judged by the investigator as ‘not related’ in causality to the Drug. In this plan, ‘adverse drug reactions or infections’ is used in headings, and ‘ADRs’ is used in the text and tables.
Serious adverse event (SAE)	[Prior-approval data] An adverse event (AE) judged as ‘serious’ by the trial investigator. [Surveillance data] An adverse event (AE) judged as ‘serious’ by the investigator. Note that events listed in the separate MedDRA code list of the Takeda Medically Significant AE List should be treated as serious even if judged as

Item	Definition
	'not serious' by the investigator.
Bleeding-related event	An event falling under Standardized MedDRA Query (SMQ) code 20000038 (hemorrhagic SMQ [narrow scope]).
Rate of patients	
[For safety compilation with safety-evaluable patients] Calculated by the following equation: $[\text{Number of Patients}] / [\text{Number of Safety-Evaluable Patients}] \times 100$.
 
[For safety compilation with safety-unevaluable patients] Calculated by the following equation: $[\text{Number of Patients}] / [\text{Number of Safety-Unevaluable Patients}] \times 100$.

Onset time	
Calculated by the following equation: $[\text{Onset Date}] - [\text{Start Date}] + 1$.
 
If the onset date is unknown, use the first day of the month as the onset date in this equation. However, use the start date as the onset date if $[\text{Start Year \& Month}] = [\text{Onset Year \& Month}]$.

Liver patient	A patient with 'fatty liver,' 'alcoholic fatty liver,' 'chronic hepatitis' or 'hepatic cirrhosis' check-marked in the Complication Details field. Or a patient with a complication falling under the SMQ code 20000005 (hepatic SMQ [narrow scope]) in the Complication Details (Other Diseases) field.
Kidney patient	A patient with 'diabetic nephropathy,' 'glomerulonephritis' or 'chronic kidney disease (CKD)' check-marked in the Complication Details field. Or a patient with a complication falling under the Takeda MedDRA query (TMQ) (Renal Disease) in the Complication Details (Other Diseases) field.
Heart patient	A patient with 'myocardial infarction,' 'angina pectoris' or 'atrial fibrillation' check-marked in the Complication Details field. Or a patient with a complication falling under the SOC code 10007541 (cardiac disorders) in the Complication Details (Other Diseases) field.
Cerebrovascular patient	A patient with 'cerebral infarction' or 'cerebral hemorrhage' check-marked in the Complication Details field. Or a patient with a complication falling under the SMQ code 20000060 (cerebrovascular SMQ [narrow scope]) in the Complication Details (Other Diseases) field.
Diabetic patient	A patient with 'diabetes' check-marked in the Complication Details field. Or a patient with a complication falling under the TMQ code (Diabetes Mellitus Confirmed diagnosis, excl diagnostics) in the Complication Details (Other Diseases) field.
Hypertensive patient	A patient with 'hypertension' check-marked in the Complication Details field. Or a patient with a complication falling under the SMQ code 20000147 (hypertensive SMQ [narrow scope]) in the Complication Details (Other Diseases) field.
Myocardial infarction	A patient with 'myocardial infarction' check-marked in the Complication

Item	Definition
patient	Details field. Or a patient with a complication falling under the SMQ code 20000047 (myocardial infarction SMQ [narrow scope]) in the Complication Details (Other Diseases) field.
Anginal patient	A patient with ‘angina pectoris’ check-marked in the Complication Details field. Or a patient with a complication falling under the MedDRA PT code 10002383 (angina pectoris), 10002388 (unstable angina pectoris), 10036759 (Prinzmetal angina), or 10058144 (postinfarction angina) in the Complication Details (Other Diseases) field.
Atrial fibrillation patient	A patient with ‘atrial fibrillation’ check-marked in the Complication Details field. Or a patient with a complication falling under the MedDRA PT code 10003658 (atrial fibrillation) in the Complication Details (Other Diseases) field.
Ischemic cerebrovascular patient	A patient with ‘cerebral infarction’ check-marked in the Complication Details field. Or a patient with a complication falling under the SMQ code 20000063 (ischemic cerebrovascular disease SMQ [narrow scope]) in the Complication Details (Other Diseases) field.
Hemorrhagic cerebrovascular patient	A patient with ‘cerebral hemorrhage’ check-marked in the Complication Details field. Or a patient with a complication falling under the SMQ code 20000064 (hemorrhagic cerebrovascular disease SMQ [narrow scope]) in the Complication Details (Other Diseases) field.
Bleeding-related event patient	A patient with a complication falling under the SMQ code 20000038 (bleeding SMQ [narrow scope]) in the Complication Details (Other Diseases) field.
Age	
Calculated by the following equation: [Start Year] - [Birth Year] - 1 if [Start Month & Day] < [Birth Month & Day].
 
Calculated by the following equation: [Start Year] - [Birth Year] if [Start Month & Day] ≥ [Birth Month & Day].
 
If the birth day is unknown, use the first day of the month instead in this equation.

BMI	Calculated by the following equation: [Weight (kg)] / (0.0001 × [Height (cm)] × [Height (cm)]). Indicated by rounding off to the first decimal place.
Disease duration (in years)	Calculated by the following equation: ([Start Year & Month] - [Year & Month of Hyperlipidemia Diagnosis] + 1) / 12. Indicated by rounding off to the first decimal place.
Start date	The start date of first administration of the Drug stated in the Treatment Duration field of the eCRF.
End date	
The end date of last administration of the Drug stated in the Treatment Duration field of the eCRF.
 
However, if the end date of last administration is in ‘ongoing 12 months after

Item	Definition
	baseline,' the end date should be the start date plus 405 days.
Observation period (in days)	Refers to the entire period of observation. The start date and end date of observation period should be the same as the 'start date' and 'end date,' respectively. Calculated by the following equation: [End Date] - [Start Date] + 1.
Treatment duration (in days)	Refers to the entire period of treatment. A total of Drug dosing periods in the number of actual administration days, excluding washout period. Calculated as a total of ([End Date] - [Start Date] + 1) in the number of actual administration days, excluding washout period.
Mean daily dose	Calculated by the following equation: Total of ([Daily Dose] × [Total Period of Treatment with the Dose]) / [Observation Period]. See the above for calculation of observation period.
Concomitant medication	A drug used during the surveillance period. However, concomitant medications exclude drugs used for adverse events occurring during the period.
Antihyperlipidemic drug	A drug starting with any of the following drug codes: 218, 2190006, 2190101, 2190102, 2190103, 2190104, 290006, 3133001, 3133400, 3399004.
Statins drug	A drug starting with any of the following drug codes: 2189010, 2189011, 2189012, 2189015, 2189016, 2189017.
Fibrate drug	A drug starting with drug code: 2183.
Intestinal transporter inhibitor	A drug starting with drug code: 2189018.
Anion-exchange resin	A drug starting with any of the following drug codes: 2189009, 2189014.
Nicotinic acid derivative	A drug starting with any of the following drug codes: 2189004, 2189005, 2190006.
Probucol	A drug starting with drug code: 2189008.
Ethyl icosapentate (EPA)	A drug starting with drug code: 3399004.
Anticoagulant drug	A drug starting with any of the following drug codes: 333, 2190408, 6343424.
Antiplatelet drug	A drug starting with any of the following drug codes: 3399 (excluding 3399004), 2171010, 2171402.
Anticoagulant/antiplatelet drug	A drug that falls under the class of either anticoagulant or antiplatelet drugs
LDL cholesterol (Friedewald formula) (mg/dL)	Calculated the equation below if the patient is fasting at the time of blood collection for laboratory testing with triglyceride 400 mg/dL or over. Indicated by rounding off to an integer alone. Total cholesterol - HDL cholesterol - triglyceride / 5
Non-HDL cholesterol (mg/dL)	Calculated by the equation below if triglyceride is 400 mg/dL or over. Indicated by rounding off to an integer alone. Total cholesterol - HDL cholesterol

Item	Definition
TC/HDL-C ratio	Calculated by the equation below. Indicated by rounding off to the first decimal place. Total cholesterol / HDL cholesterol
LDL-C/HDL-C ratio	Calculated by the equation below. Indicated by rounding off to the first decimal place. LDL cholesterol (Friedewald formula) / HDL cholesterol
LDL-C/Apo-B ratio	Calculated by the equation below. Indicated by rounding off to the first decimal place. LDL cholesterol (Friedewald formula) / Apo-B (fasting)
Summary statistics	Number of patients, mean value, standard deviation, minimum value, first quartile, median, third quartile, maximum value

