2.4.12 Onset Status of Adverse Drug Reactions or Infections by Complications

Statistical Analysis Set	Safety-evaluable patients in this special drug use surveillance
Details of Statistical Analysis	Compile ADR types by presence or absence of complications. The compilation method of ADR types is the same as described in section 2.4.1.
Figure/Table No.	Table 2.4.12

2.4.13 Onset Status of Adverse Drug Reactions or Infections by Presence or Absence of Hypertension

Complications

Statistical Analysis Set	Safety-evaluable patients in this special drug use surveillance
Details of Statistical Analysis	Compile ADR types by presence or absence of hypertension complications. The compilation method of ADR types is the same as described in section 2.4.1.
Figure/Table No.	Table 2.4.13

2.4.14 Onset Status of Adverse Drug Reactions or Infections by Presence or Absence of Diabetes

Complications

Statistical Analysis Set	Safety-evaluable patients in this special drug use surveillance
Details of Statistical Analysis	Compile ADR types by presence or absence of diabetes complications. The compilation method of ADR types is the same as described in section 2.4.1.
Figure/Table No.	Table 2.4.14

2.4.15 Onset Status of Adverse Drug Reactions or Infections by Presence or Absence of Liver

Complications

Statistical Analysis Set	Safety-evaluable patients in this special drug use surveillance
Details of Statistical Analysis	Compile ADR types by presence or absence of liver complications. The compilation method of ADR types is the same as described in section 2.4.1.
Figure/Table No.	Table 2.4.15

2.4.16 Onset Status of Adverse Drug Reactions or Infections by Presence or Absence of Kidney

Complications

Statistical Analysis Set	Safety-evaluable patients in this special drug use surveillance
Details of Statistical Analysis	Compile ADR types by presence or absence of kidney complications. The compilation method of ADR types is the same as described in section 2.4.1.
Figure/Table No.	Table 2.4.16

2.4.17 Onset Status of Adverse Drug Reactions or Infections by Presence or Absence of Cardiac

Complications

Statistical Analysis Set	Safety-evaluable patients in this special drug use surveillance
Details of Statistical Analysis	Compile ADR types by presence or absence of cardiac complications. The compilation method of ADR types is the same as described in section 2.4.1.
Figure/Table No.	Table 2.4.17

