2.4.35 Changes in Laboratory Test Values (Glucose Metabolism) <With Diabetic Complications>

Statistical Analysis Set	Safety-evaluable patients in this special drug use surveillance
Details of Statistical Analysis	Calculate summary statistics at each evaluation timepoint for fasting blood glucose (mg/dL) and HbA1c (NGSP value) (%) measurements and variations from baseline. In addition, calculate the 95% confidence interval for the mean value for variations from baseline.
Remarks	Stratification factor: With diabetic complications
Figure/Table No.	Table 2.4.35

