2.4.36 Changes in Laboratory Test Values (Glucose Metabolism) <Without Diabetic Complications>

Statistical Analysis Set	Safety-evaluable patients in this special drug use surveillance
Details of Statistical Analysis	Calculate summary statistics at each evaluation timepoint for fasting blood glucose (mg/dL) and HbA1c (NGSP value) (%) measurements and variations from baseline. In addition, calculate the 95% confidence interval for the mean value for variations from baseline.
Remarks	Stratification factor: Without diabetic complications
Figure/Table No.	Table 2.4.36

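### SAP 1.1 does not count the 'diabetic nephropathy' check-mark as diabetes, so a patient with only that box ticked, if the eCRF allows it, is analysed as non-diabetic

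*SAP*

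**What the plan says.** SAP 1.1 defines a diabetic patient by two routes. The first is a check-box: "A patient with 'diabetes' check-marked in the Complication Details field". The second is a coded free-text entry, that is, a complication "falling under the TMQ code (Diabetes Mellitus Confirmed diagnosis, excl diagnostics) in the Complication Details (Other Diseases) field". The query is applied to the Other Diseases entries, not to the check-boxes.

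The same section defines a kidney patient, again by check-box or by a coded term. The check-box route reads: "A patient with 'diabetic nephropathy,' 'glomerulonephritis' or 'chronic kidney disease (CKD)' check-marked in the Complication Details field". So "diabetic nephropathy" is a box of its own in the Complication Details field, and the kidney definition is the only one that uses it.

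Diabetic status then feeds these outputs:

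- SAP 2.4.35 and 2.4.36 each summarise "fasting blood glucose (mg/dL) and HbA1c (NGSP value) (%) measurements and variations from baseline", with a 95% confidence interval for the mean change. Their remarks are "Stratification factor: With diabetic complications" and "Stratification factor: Without diabetic complications" respectively.
- SAP 2.4.14: "Compile ADR types by presence or absence of diabetes complications".
- SAP 2.2 and 2.4.8 list Diabetic as one category of the complication breakdown.

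The diabetic and kidney definitions are in substance the same in the superseded SAP versions. Protocol 9.2 collects complications at baseline but gives no rule on how one ticked complication bears on another.

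**The concern.** A site may tick the nephropathy box as the more specific diagnosis and leave the general 'diabetes' box empty. Under the SAP's rules that patient is a kidney patient and, at the same time, not diabetic. These two statements cannot both be right, because a diagnosis of diabetic nephropathy presupposes diabetes.

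What is at stake is the purity of the two glucose strata. Values from a patient with diabetes would sit in the table headed as being without it and would be missing from the companion table. The ADR comparison in Table 2.4.14 would have the same patient on the wrong side.

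**Working it through.** The plan has no figure to reproduce here. The check has two steps: apply the definitions as logical rules, then show how far a few misfiled patients could move the stratum mean.

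**Step 1. The rules.** The inputs are the definitions in SAP 1.1.

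- Current rule: diabetic = ('diabetes' box) OR (diabetes-query term in Other Diseases).
- Rule with the addition: diabetic = ('diabetes' box) OR ('diabetic nephropathy' box) OR (diabetes-query term in Other Diseases).

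The kidney column below shows the contribution of the nephropathy box alone.

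| 'Diabetes' box | Nephropathy box | Query term in Other Diseases | Kidney | Diabetic now | Diabetic with addition |
|---|---|---|---|---|---|
| no | no | no | no | no | no |
| no | no | yes | no | yes | yes |
| no | **yes** | no | yes | **no** | **yes** |
| no | yes | yes | yes | yes | yes |
| yes | no | no | no | yes | yes |
| yes | no | yes | no | yes | yes |
| yes | yes | no | yes | yes | yes |
| yes | yes | yes | yes | yes | yes |

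Exactly 1 of the 8 combinations changes: nephropathy ticked, 'diabetes' not ticked, and no diabetes term written under Other Diseases. The consequences for that patient are:

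| Output | As written | With addition |
|---|---|---|
| Tables 2.4.35 / 2.4.36 | in 2.4.36 (without) | in 2.4.35 (with) |
| Table 2.4.14 | absence | presence |
| Tables 2.2 and 2.4.8, Diabetic row | left out | included |

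Tables 2.2 and 2.4.8 have no category for absence of diabetes. There the patient is omitted from a row and is not counted in a wrong one.

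**Step 2. Size.** Let f be the share of the 'without' stratum that is misfiled and d the excess of their mean HbA1c over that of the rest, μ. The stratum mean is (1 − f)μ + f(μ + d) = μ + f·d, so the shift is f·d. The documents give neither f nor d, so both are assumptions:

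| Assumed f | d = 1.0 point | d = 1.5 points |
|---|---|---|
| 0 | 0 | 0 |
| 0.5% | 0.005 | 0.0075 |
| 1% | 0.010 | 0.015 |
| 2% | 0.020 | 0.030 |
| 5% | 0.050 | 0.075 |

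This is a shift in level. The same algebra applies to mean change from baseline: if the misfiled patients' mean change differs from the others' by δ, the shift is f·δ. Nothing in the documents gives δ, so no bias in mean change can be shown.

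**The case against.** The strongest objection is that the case may never arise. The eCRF is not among the documents. An edit check, a nested box or a completion guide may force the 'diabetes' tick, and sites may tick both boxes anyway. Protocol 7.4 also lets the sponsor review entries and ask for re-survey, and SAP 1.1 counts a patient as locked only after an approval process. A lone nephropathy tick is a visible inconsistency that could be queried then. This stands as a limit on the number affected. It does not repair the definition, because no text requires such a query or mentions an edit check.

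Second, the remarks in 2.4.35 and 2.4.36 do not cite the diabetic-patient definition. That is true, but it is the only definition of diabetic status in the SAP. Whether the label means diabetes as a comorbidity or complications arising from diabetes, a patient with diabetic nephropathy belongs in the 'with' table.

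Third, the outputs are descriptive. The current SAP specifies no test for them. Medians and quartiles, which move little for a few unusual values, are reported too, and the unstratified Table 2.4.34 is untouched. All of this stands and keeps the point minor.

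One defence does not succeed: that each tick is deliberately confined to one group. SAP 1.1 lets the myocardial infarction, angina and atrial fibrillation ticks count for the heart group and for their own subgroups, and does likewise for the cerebrovascular ticks.

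A reader might infer that the interval for mean change in Table 2.4.36 is seriously widened. That would need the SD of change in both groups, which the documents do not give. Suppose SDs of 0.25 and 0.9, equal mean change in the two groups, and 5% misfiled. The SD becomes √(0.95 × 0.25² + 0.05 × 0.9²) = 0.316, a ratio of 1.26. In an assumed stratum of 1,000 to 200 patients the half-width then grows by 1.96 × (0.316 − 0.25)/√n, about 0.004 to 0.009 HbA1c points. The percentage sounds large, but it rests wholly on unsourced inputs and is small in absolute terms.

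**Conclusion.** The gap in the definition is real and follows from the text: a patient with only the nephropathy box ticked, and no diabetes term under Other Diseases, is classed as not diabetic. Whether any such patient exists depends on an eCRF that the documents do not show, and the number may be zero.

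If they make up 0.5% to 5% of the 'without' stratum and their HbA1c is 1.0 to 1.5 points higher (both assumptions), the stratum mean rises by about 0.005 to 0.075 points. This is a minor point.

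Two stronger readings are not supported. A reader might suppose that these patients have advanced, drug-treated diabetes and so bring treatment effects into the stratum, but the documents do not describe them. A reader might also suppose that the two tables were set up to isolate a drug effect on glucose in non-diabetic patients, but the SAP states no such purpose.

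**What to change.** In SAP 1.1, define a diabetic patient as one with 'diabetes' or 'diabetic nephropathy' check-marked, or with a coded term as now. Leave the nephropathy tick in the kidney definition as well. Re-derive Tables 2.2, 2.4.8, 2.4.14, 2.4.35 and 2.4.36.

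The cost is one phrase and a re-run of five tables, and no new data are needed because both ticks are already collected. If no patient has the lone tick, no result changes.

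An equal remedy is to state in the SAP that an eCRF check forces the 'diabetes' tick whenever 'diabetic nephropathy' is ticked, if such a check exists.
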